11.5.2. Patient Global Impression Scores

- **Patient Global Impression of Health** (PGI-H). Participants report their overall impression of their health status today on the following scale: 0 Very poor, 1 Poor, 2 Fair, 3 Good, 4 Very good.
- **Patient Global Impression of Severity** (PGI-S). Participants rate the severity of their respiratory illness on the following scale: 0 I feel fine (no respiratory illness), 1 I feel a little ill, 2 I feel very ill, 3 I feel extremely ill.
- **Patient Global Impression of Change** (PGI-C). Participants rate the amount of change in their health each day during an ARI episode on the following scale: -3 Very much better, -2 Much better, -1 A little better, 0 About the same/no change, 1 A little worse, 2 Much worse, 3 Very much worse
- **Return to Usual Health**. Participants are being asked whether they have returned to their usual health after developing symptoms suggesting an ARI.

11.6. Lawton-Brody Instrumental Activities of Daily Living (IADL) Scale

The Lawton-Brody IADL questionnaire ([Attachment 8](#)) covers 8 domains. Women are scored on all 8 domains; historically, for men, the domains of food preparation, housekeeping, and laundering are excluded from the analysis. Participants are scored according to their highest level of functioning in that category (either 0 or 1). A summary score ranges from 0 (low function, dependent) to 8 (high function, independent) for women, and from 0 through 5 for men.

Change from baseline independence status associated with ARI collected using the Lawton-Brody IADL questionnaire will be descriptively analyzed.

11.7. Frailty Index Score

The frailty index score will be calculated from the medical conditions of interest, RiiQ, and the Lawton-Brody IADL. More details will be provided in the SAP.

The change from baseline in frailty index score will be determined. The following correlations will be explored (descriptively or graphically):

- the correlation between the baseline frailty index score and RSV infection incidence, severity (as determined from the RiiQ questionnaire) and duration.
- the correlation between the baseline frailty index score and the primary endpoints.
- the correlation between the change in frailty index score and presence of an RSV ARI.

11.8. Clinical Assessment

Symptoms from the clinical assessment will be scored on a 4-point scale (from 0 through 3), with higher scores indicating greater severity. The scores will be analyzed descriptively.

11.9. Immunogenicity Analyses

No formal statistical testing of the immunogenicity data is planned. All immunogenicity analyses will be performed on the PPI population. Key tables might be repeated for the FAS (including samples that are excluded from the PPI analysis).

11.9.1. Immuno Subset

No formal hypothesis on immunogenicity will be tested. Descriptive statistics (geometric mean and 95% CI for ELISA and RSV neutralization assay; median and quartiles for IFN- γ ELISpot and ICS) will be calculated for continuous immunologic parameters at all time points. For the humoral assays, geometric mean fold rises from baseline and corresponding 95% CIs might additionally be calculated. Baseline is considered as the last available assessment before the vaccination. Graphical representations of immunologic parameters will be made as applicable.

The impact of baseline factors on the humoral and cellular responses will be explored graphically or via descriptive statistics.

11.9.2. Revaccination Subcohorts

No formal hypothesis on immunogenicity will be tested for Revaccination Subcohorts. Descriptive statistics (geometric mean and 95% CI for ELISA and RSV neutralization assay, median and quartiles for IFN- γ ELISpot) will be calculated for continuous immunologic parameters at all time points. Geometric mean fold rises from baseline and corresponding 95% CIs might additionally be calculated. Geometric mean ratios and corresponding 95% CIs between Day 15 post first vaccination and Day 15 post second vaccination within the group receiving active study vaccine

on Day 1 and the day of the second vaccination depending on the Revaccination Subcohort will be calculated for the different assays.

In addition, the GMT ratios with corresponding 95% CIs of Day 15 post second vaccination for the group receiving active study vaccine twice versus the group receiving placebo first and active study vaccine 1, 2, or 3 years later will also be calculated for the different assays. Therefore, an analysis of variance (ANOVA) model will be fitted with the respective titers as dependent variable and group as independent variable. The estimate and CIs obtained as such will be back transformed (by exponentiation) to a GMT ratio and the corresponding CI. As a sensitivity analysis, different variances between the groups will be allowed, therefore the CIs will be calculated via Welsh's ANOVA.

For Revaccination Subcohorts 2A and 2B that get a third vaccination with Ad26.RSV.preF/RSV preF protein mixture or with the individual vaccine components, no formal hypothesis is tested; descriptive statistics over time after the third vaccination will be calculated.

Graphical representations of immunologic parameters will be made as applicable.

The impact of baseline factors on the humoral responses will be explored graphically or via descriptive statistics.

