
 • To explore the impact of baseline frailty and functioning in Instrumental Activities of Daily Living (IADL) on the incidence, severity, and duration of RT-PCR confirmed RSV-mediated LRTD 	
 • Assessment of RSV incidence (by RT-PCR), RSV severity (per RiiQ questionnaire), and duration of ARI episode(s) in relation to the baseline frailty score and baseline Lawton-Brody IADL

^a The Respiratory Infection Intensity and Impact Questionnaire used in this study is the RiiQ™ Version 2, 2018 (hereafter referred to as RiiQ).

 • In Revaccination Subcohorts 2A and 2B, to explore the relative contribution of each component of the active vaccine on safety and reactogenicity in terms of solicited local and systemic AEs during 7 days after revaccination, and in terms of unsolicited AEs during 28 days after revaccination 	
 • Occurrence, severity, duration, and relationship to vaccination of solicited local and systemic AEs during 7 days after revaccination and of unsolicited AEs during 28 days after revaccination

 • In Revaccination Subcohorts 2A and 2B, to explore the relative contribution of each component of the active vaccine on humoral and cellular immunogenicity following revaccination 	
 • Characterization of the humoral and cellular immune response following revaccination, with emphasis on neutralizing and binding antibodies

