For all medically attended ARIs, including those resulting in hospitalization, a standard question list will be provided, with the aim to collect additional information ([Attachment 12](#)) on any other diagnostics (eg, chest x-rays, spirometry, pulmonary function tests, etc.) or interventions during the clinical course of the ARI. Every effort should be made to collect data on the clinical course of ARIs, including information on hospitalization, oxygenation status, supplemental oxygen requirements and specific drug treatments, as well as other concurrent respiratory illness present at the time of symptom onset and up to symptom resolution. If an expected eDiary recording has been missed by a participant, a member of the staff should contact the participant the next morning to confirm that eDiaries are being completed as required. Telephone calls to or telemedicine contacts with the participants to facilitate compliance with the study procedures between study visits are encouraged.

For participants who experience symptoms suggesting an ARI episode, RT-PCR assay of the midturbinate nasal swabs and sputum sample (when available) taken after symptom onset will be used to determine whether the infection was caused by RSV^a. If at least one of these samples is positive for RSV, the collected information will be applied against the clinical case definitions for RSV-mediated LRTD. For participants hospitalized with symptoms of an ARI, confirmation of RSV infection using a Food and Drug Administration (FDA)-approved RT-PCR test at the local (hospital) laboratory will also be obtained.

Site staff and participants will remain blinded as to the outcome of the RT-PCR test results until study unblinding, but participants and their routine health care professional (HCP) can obtain external diagnostics, including RSV RT-PCR, as medically needed.

Collection of ARI data by the study site will be ceased for that particular episode if a participant has tested positive for SARS-CoV-2 (by a local test that is FDA-approved or by central laboratory PCR).

Immunogenicity

Blood will be collected from all participants for humoral immunogenicity assessments before vaccination on Day 1, and 14 days and 1 year after vaccination on Day 1. These samples will be used for humoral immunogenicity assessments for participants experiencing an ARI episode during the RSV season.

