Table 9 shows the actual distance from the mean to the limits of 95% CI around the Day 15 post second vaccination ratio between the 2 groups, for the different assays. The calculations consider an exclusion rate of 10% from the sample size of revaccinated participants (~108 participants per group for Revaccination Subcohorts A and C, and ~120 participants per group for Revaccination Subcohort B).

Table 9: Distance From the Mean to the Limits of 95% CI Around the Ratio on Day 15 Post Second Vaccination Between the 2 Groups for Pre-F ELISA, VNA A2, and ELISpot

Revaccination Subcohort	Assay	N (per group)	Distance ^a from Mean to Limits 95% CI	95% CI if Observed Ratio is 1
A and C	Pre-F ELISA (SD=1.3)	120	0.349	(0.79;1.27)
	VNA (SD=1.5)	120	0.402	(0.76;1.32)
	ELISpot (SD=1.2)*	50	0.476	(0.72; 1.39)
B	Pre-F ELISA (SD=1.3)	135	0.331	(0.79;1.26)
	VNA A2 (SD=1.5)	135	0.381	(0.77; 1.30)
	ELISpot (SD=1.2)	135	0.305	(0.81; 1.24)

CI = confidence interval, ELISA = enzyme-linked immunosorbent assay, ELISpot = enzyme-linked immunospot (assay), SD = standard deviation, VNA = virus neutralization assay

^a Calculated on the log₂-scale.

*: No PBMC samples are taken for Revaccination Subcohort A.

Safety

With ~240 active study vaccine participants in Revaccination Subcohorts A and C, and ~270 active study vaccine participants in Revaccination Subcohort B, the observation of 0 events in the database would be associated with 95% confidence that the true rate is <1.5%.

Table 10 shows the probabilities of observing at least 1 AE in one of the arms at given true AE rates in the Revaccination Subcohorts.

Table 10: Probability of Observing at Least 1 Adverse Event or Serious Adverse Event at a Given True Adverse Event Rate in the Revaccination Subcohorts

True Adverse Event Rate	Revaccination Subcohorts A and C		Revaccination Subcohort B	
	Overall	Per Group	Overall	Per Group
	N=240 ^a	N=120 ^a	N=270 ^a	N=135 ^a
0.1%	21%	11%	24%	13%
0.5%	70%	45%	74%	49%
1%	91%	70%	93%	74%
2.5%	>99.9%	95%	100%	97%

^a Approximate number

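### The post-second-dose GMT ratio in the revaccination subcohorts is valid but unadjusted for the Day 1 titre and strata already at hand; separately, the re-randomised third-dose arms get no between-arm ratio

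*Protocol*

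**What the plan says.** Protocol Section 11.9.2 plans "the GMT ratios with corresponding 95% CIs of Day 15 post second vaccination", comparing participants vaccinated with active vaccine twice with those given placebo first and active vaccine one, two or three years later. For this, "an analysis of variance (ANOVA) model will be fitted with the respective titers as dependent variable and group as independent variable". The only variant is a sensitivity analysis that allows unequal variances. Baseline factors are otherwise looked at graphically or descriptively. There is no test: "No formal hypothesis on immunogenicity will be tested for Revaccination Subcohorts".

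The material for adjustment exists. Section 9.1.1 states: "Blood will be collected from all participants for humoral immunogenicity assessments before vaccination on Day 1". Section 5 stratifies the randomisation by age category and by increased risk of severe RSV disease, and Section 11.4.1.1 puts both factors into the primary efficacy model.

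For the third dose, Section 5 re-randomises subcohorts 2A and 2B 1:1:1, blinded, to the mixture or one of its two components. The exploratory objective in Section 2.1 reads: "In Revaccination Subcohorts 2A and 2B, to explore the relative contribution of each component of the active vaccine on humoral and cellular immunogenicity". The matching analysis text in Section 11.9.2 is: "no formal hypothesis is tested; descriptive statistics over time after the third vaccination will be calculated".

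**The concern.** Two separate matters arise.

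**Second dose.** Subcohort members consent separately, one to three years after randomisation, and number about 120 or 135 per group. With groups of that size, chance differences in pre-existing RSV immunity carry through to an unadjusted ratio. The Day 1 pre-dose titre precedes every study vaccination, so it can be used as a covariate without disturbing the comparison. Leaving it out gives up precision and some protection against chance imbalance. How much depends on how strongly it predicts the post-second-dose titre.

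**Third dose.** This is a matter of a missing contrast, not of lost precision. The re-randomisation sets up a comparison between arms, and the objective is comparative in wording. In the same section the second-dose comparison receives a ratio with a 95% CI even though it is not tested, so the absence of a hypothesis does not explain why the third-dose comparison has none.

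**Working it through.** **Inputs.** Log2-scale SDs of 1.3 (pre-F ELISA), 1.5 (VNA) and 1.2 (ELISpot), and 10% exclusion leaving about 108 per group in A and C and about 120 in B, from Section 11.2.4. Third-dose arms of 40 (2A) and 45 (2B), from Table 2. The correlation r between the Day 1 pre-dose and Day 15 post-second-dose log2 titres is not in the documents; it is assumed over 0.2 to 0.7.

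**Step 1: reproduce Table 9.** Unadjusted half-width = t(0.975; 2n−2) × SD × √(2/n).
- A and C, n = 108: ELISA 0.3487 (stated 0.349); VNA 0.4024 (stated 0.402).
- B, n = 120: ELISA 0.3306 (0.331); VNA 0.3815 (0.381); ELISpot 0.3052 (0.305).
- A/C ELISpot: 0.4763 at n = 50 (stated 0.476). That row is reproduced only without the 10% exclusion; at n = 45 it would be 0.5027.

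So the planned precision is that of the unadjusted model.

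**Step 2: adjust for the Day 1 titre (humoral assays).** Half-width = t(0.975; 2n−3) × SD × √(1−r²) × √(2/n).

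| | unadjusted | r = 0.2 | r = 0.3 | r = 0.5 | r = 0.7 |
|---|---|---|---|---|---|
| √(1−r²) | 1 | 0.980 | 0.954 | 0.866 | 0.714 |
| A/C ELISA | 0.349 | 0.342 | 0.333 | 0.302 | 0.249 |
| A/C VNA | 0.402 | 0.394 | 0.384 | 0.348 | 0.287 |
| B ELISA | 0.331 | 0.324 | 0.315 | 0.286 | 0.236 |
| B VNA | 0.381 | 0.374 | 0.364 | 0.330 | 0.272 |

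The intervals narrow by about 2%, 5%, 13% and 29%. On the ratio scale, the A/C ELISA interval around 1 goes from 0.79–1.27 to 0.81–1.23 at r = 0.5. No gain has been computed for the strata.

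**Step 3: which assays have a Day 1 value.** Section 3.1 bars members of A and B from having been in the Immuno Subset. Section 9.2.2 places cellular sampling in 2A after the third vaccination and in B after the second and third, and in C only in a subset of about 100. So A and B have no Day 1 cellular sample, and C has one only for any former Immuno Subset members. The Day 1 covariate therefore serves ELISA and VNA, not ELISpot.

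**Step 4: third-dose ratios.** Assume the same 10% exclusion: 40 × 0.9 = 36 per arm in 2A, and 45 × 0.9 = 40.5, taken as 40, in 2B. Pairwise half-widths by the step 1 formula, with the interval around a ratio of 1:
- 2A: ELISA 0.611 (0.65–1.53); VNA 0.705 (0.61–1.63).
- 2B: ELISA 0.579 (0.67–1.49); VNA 0.668 (0.63–1.59).

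If the pre-third-dose titre correlated 0.5 with the outcome (again an assumption), these would become 0.529, 0.611, 0.501 and 0.578.

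**The case against.** The strongest reply is that nothing here is in error. An unadjusted ANOVA on log titres gives a valid ratio and interval, it matches Table 9, and no decision or error rate depends on the interval width in an untested, exploratory analysis. That stands, and it limits the point to an improvement.

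Four stronger readings are tempting and are not supported:
- A reader might take the correlation of 0.5 from Table 8 and conclude that adjustment is worth a third more participants (108/(1−0.25) = 144). That 0.5 links two post-vaccination Day 15 titres. It says nothing about a pre-dose titre and a response one to three years later, and at r = 0.2 the gain is close to nil.
- A reader might infer that the unadjusted ratio is biased because members volunteer. Sections 3.2 and 5 keep sites and participants blind to the Day 1 allocation at the second dose, so allocation was not disclosed to those deciding to join. Chance imbalance is already reflected in the confidence interval. Adjustment reduces it but would not remove every selection effect.
- A reader might see a defect in modelling titres and then exponentiating. Tables 8 and 9 are on the log2 scale and the result is a GMT ratio, so the intended scale is clear.
- A reader might say that the component objective has no estimate at all. Section 11.9.2 plans geometric means with 95% CIs at all time points for ELISA and neutralisation, so the arms can be set side by side. Only the direct contrast is missing.

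**Conclusion.** The point holds as a modest, low-cost improvement, not as the correction of an error. For ELISA and VNA, the group-only model forgoes between about 2% and 29% of interval width, depending on a correlation that the documents do not give and that is assumed here to lie between 0.2 and 0.7. It also forgoes some protection against chance imbalance. For ELISpot the Day 1 titre is not a usable covariate, so only the strata are available.

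The third-dose point stands separately. A blinded 1:1:1 re-randomisation made to explore component contributions deserves a stated between-arm ratio. At 36 to 40 per arm it will be wide, about 0.61 to 1.63 for VNA in 2A without adjustment, and it should be read as descriptive.

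**What to change.** In Section 11.9.2:

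1. For ELISA and VNA, estimate the Day 15 post-second-vaccination GMT ratio from ANCOVA on log2 titre with group, Day 1 pre-dose log2 titre, age category and risk stratum. Do not adjust for the pre-revaccination titre, because the Day 1 assignment affects it.
2. For ELISpot, adjust for the strata only.
3. For 2A and 2B after the third dose, add descriptive GMT ratios with 95% CIs, mixture versus each component, from ANCOVA on log2 titre with the pre-third-dose titre as covariate. That sample precedes the third dose, so the assigned component cannot have affected it. Keep these ratios untested.

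The cost is revised wording, slightly more analysis work, and a simple rule for missing baseline titres. No new samples or visits are needed.

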11.9.3. Correlates of Risk

If VE is demonstrated, correlates of risk will be explored. More details with appropriate methods will then be provided in a separate SAP.

11.10. Medical Resource Utilization Analyses

Medical resource utilization data will be descriptively summarized by intervention group.

11.11. Safety Analyses

No formal statistical testing of safety data is planned. Safety data by vaccination group and based on the FAS will be analyzed descriptively. The analysis of solicited and unsolicited AEs will be restricted to a subset of the FAS (ie, the Safety Subset). For SAEs, the complete FAS is considered. The impact of baseline factors (eg, being at increased risk for severe RSV disease) might be explored as well. Additionally, the analysis of solicited and unsolicited AEs and AESIs (if collected) will also be performed for each of the Revaccination Subcohorts and will be restricted to participants of the Revaccination Subcohorts that are part of the FAS.

Adverse Events (Solicited and Unsolicited)

The verbatim terms used in the eCRF by investigators to report AEs will be coded using the Medical Dictionary for Regulatory Activities (MedDRA). All reported AEs with onset during the active vaccination phase (ie, AEs occurring after vaccination up to 28 days post-vaccination), and all SAEs and AESIs will be included in the analysis. For each AE, the number and percentage of participants who experience at least 1 occurrence of the given event will be summarized by group.

Solicited local (at the injection site) and systemic AEs will be summarized descriptively. The overall frequencies per group as well as frequencies according to severity and duration will be calculated for solicited AEs.

Summaries, listings, datasets, or participant narratives may be provided, as appropriate, for those participants who die, who discontinue the study (or study vaccination, if applicable) due to an AE, or who experience a severe AE, an SAE, or an AESI.

Any ARI recorded as an (S)AE in the eCRF will be excluded from any AE analysis if the laboratory RT-PCR is subsequently found to be positive for RSV. ARIs arising from RSV infection will not be reported as (S)AEs in the Clinical Study Report as they are endpoints of the study and will be tabulated separately.

Vital Signs

A tabulation of the distribution of temperatures in the 7 days after vaccination, per half degree intervals, will be provided. For systolic and diastolic blood pressures, pulse rate and respiratory rate, the percentage of participants with values beyond clinically relevant limits will be summarized.

Physical Examination

Abnormalities resulting from a physical examination will be documented as medical history or as AE. Therefore, no physical examination specific tables or listings will be generated for Day 1. Abnormalities resulting from a physical examination on other timepoints will be listed.

